9.2.2 Selection and Number of Sites

Sites participating in Study 20120215 may be selected (planned in Europe, Israel, Australia, and Latin America) and further centers located in (but not limited to) Europe, Israel, Australia, Brazil, Canada, Mexico, United States, outside of Study 20120215 are planned to be included in this 20180130 study. The final number (and locations) of sites has not been confirmed.

9.2.3 Patient Eligibility

9.2.3.1 Inclusion Criteria

Patients are eligible to be included in the study if they meet all of the following inclusion criteria.

- Paediatric B-cell precursor ALL patients with any indication world-wide that received blinatumomab or chemotherapy in routine clinical practice, followed by transplantation, or EU paediatric indications that may be authorized in the future. This means that paediatric patients which receive blinatumomab off-label in the EU or with a different indication in ex-EU regions may be included in the study.
- Patient's legally acceptable representative has provided informed consent when the patient is legally too young to provide informed consent and the patient has provided written assent based on local regulations and/or guidelines prior to any study-specific activities/procedures being initiated.

9.2.3.2 Exclusion Criteria

NA

9.2.4 Baseline Period

The baseline period will be considered as the time between initial diagnosis of ALL and the alloHSCT. Specific clinical and treatment characteristics will be collected at specific time points during baseline (eg, at diagnosis, prior to SOC/blinatumomab therapy, up to alloHSCT transplant, etc).

9.2.5 Study Follow-up

This is a prospective study where data will be collected at routine clinical visits which will occur per standard of care (for a period of up to 12 years). A total of 12 years follow-up or 144 months of follow-up is planned for study 20180130. At each data collection stage, relevant information will be retrieved from patient charts subsequent to the preceding data abstraction time point to ensure there is no gap in data collection. Data abstraction will be performed approximately every 6 months (± 30 days) starting at enrolment. Additional data on neuropsychomotor development will be assessed through specific questionnaires (paper and/or electronic) which will be administered at pre-specified intervals starting from enrolment (approximately every 6 months [± 30 days] for patients up to 6 years old and approximately yearly [± 60 days] for patients from 6 years old). For each enrolled patient, data collection will end at 12-years of follow-up, the age of 25 years, loss-to-follow-up, withdrawal of consent, or death, whichever occurs earliest. All treatments for ALL will be captured in this period.

9.3 Variables

9.3.1 Outcome Assessment

Primary Objective

- Impairment is defined as any of the following:
 - o Neuropsychomotor development impairment in the areas of:
 - Social and emotional
 - Language/communication
 - Cognitive (learning, thinking, problem-solving)
 - Motor (both gross and fine motor development)
 - As lower scores on adaptive functioning measures indicate greater deficits (ie, lower day-to-day functioning), impairment will be defined as performance falling 2 or more standard deviations below the normative population mean in 1 or more adaptive functioning domain(s) (ie, motor, language, social skills).

- As higher scores on executive function (ie, cognitive) measures indicate greater deficits (ie, more problematic thinking), impairment will be defined as performance falling 2 or more standard deviations above the normative population meant in 1 or more executive function domain(s). For motor skills of patients ages 10 years and older, impairment will be defined as having an age-equivalency a year or more below their chronological age, as further development is not expected beyond that age and normative data is limited.
- Individual change over time across domains will also be assessed for significance. Specifically, it is anticipated that patients will have their own respective baseline level of skills across assessed areas. For example, some individuals may have significantly above average day-to-day functioning and/or cognitive skills at the start of the study. Thus, the formal definition of psychomotor 'impairment,' placing two or more standard deviations below the mean, will not capture meaningful changes amongst these patients. To account for this, analysis will also examine statistically significant changes over time within each person's own scores across psychomotor domains. Changes that are two or more standard deviations from one's own baseline will be considered relevant adverse effects.
- For all patients, the Vineland Adaptive Behavior Scales-Third Edition (Vineland-3) Comprehensive Parent/Caregiver Form will be used. The Vineland-3 is a widely used and validated measure of adaptive behavior across core areas of Communication (receptive, expressive, and written language), Daily Living Skills (personal, domestic, and community), Socialization (interpersonal relationships, play and leisure, and coping skills), and Motor Skills (gross motor and fine motor) (Sparrow et al, 2016). An additional section on Maladaptive Behaviors is included that assesses for problem behaviors related to internalizing (eg. anxiety, depression) and externalizing (eg, aggression, conduct problems, psychosis) conditions. The Vineland-3 will be re-administered to patients ages 0-5 years every 6 months in order to capture the more rapid rate of typical development; parents (guardian) of patients (or other informant, for adult patients) ages 6 years and older will complete the form every year.
- Cognitive skills are indirectly captured by the Vineland-3 particularly for children under the age of 2 via its assessed domains. To supplement assessment of more advanced cognitive skills for patients ages 2+ the Behavior Rating Inventory of Executive Function (BRIEF) will also be used. This form is similarly well-validated and widely used to assess executive functions in paediatric and adult populations (Gioia, Isquith,Guy, & Kenworthy, 2015). The preschool form (BRIEF-P) is available for ages 2-5 and assesses higher-order cognitive skills in the areas of Inhibitory Self-Control, Flexibility, and Emergent Metacognition (eg, inhibit, shift, emotional control, working memory, plan/organize). The parent form (BRIEF-2) is applicable for ages 6-18 and assesses areas of Behavioral

Regulation (inhibit, self-monitor), Emotion Regulation (shift, emotional control), and Cognitive Regulation (initiate, working memory, plan/organize, task monitor, organization of materials). For patients ages 19+, the informant report form will be completed by a parent (guardian) or other adult who knows the patient well (BRIEF-A Informant); skills are evaluated in the areas of Behavioral Regulation (inhibit, shift, emotional control, self-monitor) and Metacognition (initiate, working memory, plan/organize, task monitor, organization of materials). The BRIEF will be re-administered to patients ages 2-5 years every 6 months in order to capture the more rapid rate of typical development; parents (guardian) or informants of patients ages 6 years and older will complete the form every year.

- A complete written manual describing administration and scoring procedures will be created by study neuropsychologist who has thorough knowledge of and experience with these measures. Initial personalized training of these procedures with study personnel will also be provided, along with ongoing consultation as needed.
- Neurological impairment defined as:
 - Peripheral nervous system disorders (including neuromuscular junction)
 - Central nervous system disorders
- Endocrine impairment defined as:
 - Hypothalamus-Pituitary-Gonadal Axis disorders
 - Hypothalamus-Pituitary-Adrenal (HPA) Axis disorders
 - Hypothalamus-Pituitary-GH Axis disorders
 - Hypothalamus-Pituitary-Thyroid Axis disorders
- o Immune system impairment defined as:
 - leukopenia (neutropenia and/or lymphopenia)
 - Iow IgG
 - low IgM
 - low IgA
 - Autoimmune disorders
 - Vaccination failure

Secondary Objectives

- HSCT-related AE defined as any second malignancy; Graft versus Host Disease (GvHD); infection, and/or; relapse
 - o Acute GvHD data includes
 - Grading of disease by either National Institute of Health (NIH) or Seattle Criteria
 - Organ involvement: skin; gut; liver; lung; eye; mouth' musculoskeletal, and/or; other

- GvHD associated symptoms: thrombocytopenia (<100 G/l); eosinophilia (Absolute Eosin Count: AEC > 500x10/L); bronchiolitis obliterans; bronchiolitis obliterans organizing pneumonia (BOOP); polyserositis, and; other
- Resolution
- Chronic GvHD data includes:
 - Diagnosis based upon clinical or histological evidence
 - Diagnosis of progressive, quiescent, or de novo disease
 - Grading of disease by either NIH or Seattle Criteria
 - Organ involvement: skin; gut; liver; lung; eye; mouth' musculoskeletal, and/or; other
 - GvHD associated symptoms: thrombocytopenia (< 100 G/l); eosinophilia (AEC > 500x10/L); bronchiolitis obliterans; bronchiolitis obliterans organizing pneumonia (BOOP); polyserositis, and; other
 - Resolution
- Infection related data includes:
 - Pathogen:
 - Identification;
 - Systemic/localized (area of localization: lungs; skin; gut; brain; other)
 - Bacterial:
 - Systemic/localized (area of localization: lungs; skin; gut; brain; other)
 - Viral:
 - Type: Cytomegalovirus (CMV) infection; CMV disease; BKV; Epstein Barr Virus (EBV); Adenovirus; Varicellazoster; Hepatitis B; Hepatitis C; Herpes Simplex; Herpes (Other); other
 - Systemic/localized (area of localization: lungs; skin; gut; brain; other)
 - Fungal:
 - Possible/Probable/Proven
 - Aspergillus ssp; Candida ssp; etc.
 - Systemic/localized (area of localization: lungs; skin; gut; brain; other)
 - Parasitic systemic/localized (area of localization: lungs; skin; gut; brain; other)
- Relapse of leukemia (see definition below)
- Relapse of leukemia defined as:
 - Isolated bone marrow relapse: M3 in the absence of extramedullary involvement
 - Combined bone marrow relapse: M2 or M3 marrow and at any extramedullary manifestation of ALL
 - Extramedullary relapse
 - CNS relapse
 - Testicular relapse
 - Relapse at other sites

CONFIDENTIAL

- Long-term AE: occurrence and severity of specific AEs as defined by measurement of associated parameters but not limited to:
 - o Gastrointestinal;
 - Diarrhea
 - Vomiting
 - Stomatitis
 - Nausea
 - Hematologic;
 - Granulocytes
 - Hemoglobin
 - Leukocytes
 - Platelets
 - Dermatology/skin toxicity;
 - Changes in skin, eg, erythema, sculitis, pruritus, ulceration, etc.
 - Cardiac;
 - Arrhythmia
 - Echocardio: left ventricular systolic function (LV-SF)
 - Cardiac function
 - Pulmonary;
 - Forced Expiratory Volume in 1 second (FEV 1)
 - 25% of forced vital capacity (MEF25)
 - Hypoxia
 - Pneumonitis, pulmonary infiltrates
 - Carbon monoxide diffusion capacity (DLCO)
 - Hepatic;
 - Bilirubin
 - Serum Glutmaic Oxaloacetic Transanimase (S-GOT)/Serum Glutamic Pyruvic Transaminase (S-GPT)
 - o Renal;
 - Creatine
 - Hematuria
 - Proteinuria
 - Neurologic;
 - Peripheral neurotoxicity (from parasthesias to paralysis)
 - Central neurotoxicity (from somnolence to coma)
 - Leukoencephalopathy (by radiographic findings)
 - Encephalopathy
 - o Infection;
 - Fever
 - Pathogen and intra venous (IV) antibiotic use
 - Immunology;
 - Allergy; eg, transient, asymptomatic/symptomatic bronchospasm, serum sickness, anaphylaxis, etc.
 - o Skeletal
- Recording of secondary malignancy formation with specific diagnosis, location, and date of diagnosis
- Overall survival, defined as death after completion of transplant

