9.7.2.2.3 Analysis of the Primary and Secondary Endpoints

Patient incidence proportions (and 95% Cls) for each of the specified outcome events will be summarized. KM estimates for time to first onset of each specified event will be provided.

For the events of interest, events that occur after a relapse or secondary malignancy will be censored as it is unlikely that events that occur after relapsed and treatment for relapse could be considered related to initial chemotherapy or blinatumomab treatment for the prior disease occurrence.

A comparison between the blinatumomab versus chemotherapy group will be conducted at the final follow-up in the study pending adequate sample size is enrolled $(\geq 50 \text{ patients per arm})$ and the blinatumomab and SOC groups are comparable (eg. there is overlap between PS distributions across the two groups, or no critical differences that cannot be accounted/adjusted for). Prior to comparison being conducted, covariates listed in Section 9.3.2 will be evaluated for differences between the two groups. Any covariates that are not comparable between the two (Wald chi-square or t-test, p-value < 0.25), will be evaluated as a covariate for adjustment in the models. The primary and secondary endpoint of discrete events (eg, incidence endpoints) will be compared by a logistic regression which will generate an odds ratio and 95% confidence interval of the odds of developing an event. Endpoints that are time-to-event will be compared by a Cox regression model which will generate hazard ratio and 95% confidence interval for the risk of developing an event. Also, we will additionally conduct a propensity score weighting analysis based on the covariates collected for this study. An additional sensitivity analysis may be done to adjust for the drop-in effect of patients receiving anti-cancer medications during follow-up.

A literature review of published data at the time of the final study report will be performed for the relevant endpoints. If there is any relevant scientific data publicly available by the time when the study ends (> 12 years later), Amgen will provide a comparative analysis. If a sufficient number of patients are identified in publicly available database with information on relevant confounding factors, Amgen will conduct a direct comparative analysis, but descriptive analyses will be undertaken either way.

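### One score beyond 2 SD in any domain at any administration makes a child a case of neuropsychomotor impairment, with no confirmation and no normative background rate beside the incidence

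*Protocol*

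**What the plan says.** Section 9.3.1 sets two cut-offs on population norms. For adaptive functioning (Vineland-3), impairment is "performance falling 2 or more standard deviations below the normative population mean in 1 or more adaptive functioning domain(s". For executive function (BRIEF, from age 2), it is a score "2 or more standard deviations above the normative population meant in 1 or more executive function domain(s". For motor skills from age 10, "impairment will be defined as having an age-equivalency a year or more below their chronological age". The endpoint table in section 8.1 counts impairment in any one area, so meeting one criterion is enough.

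Section 9.2.5 schedules the questionnaires approximately every "6 months [± 30 days] for patients up to 6 years old and approximately yearly [± 60 days] for patients from 6 years old". Section 9.3.1 gives the same frequency for each instrument, for example "The BRIEF will be re-administered to patients ages 2-5 years every 6 months". For each patient, "data collection will end at 12-years of follow-up, the age of 25 years, loss-to-follow-up, withdrawal of consent, or death, whichever occurs earliest".

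Section 9.7.2.2.3 summarises patient incidence proportions with 95% confidence intervals, and "KM estimates for time to first onset of each specified event will be provided". It compares incidence endpoints by logistic regression and time-to-event endpoints by Cox regression. Events after relapse or secondary malignancy are censored.

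The protocol nowhere requires a second abnormal score or persistence. It gives no rate at which children from the norm population would meet the rule.

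**The concern.** A cut-off at 2 SD on population norms is crossed by about 2.3% of healthy children on one score. The rule takes the most extreme of several domain scores at each administration, and first-onset counting then takes the most extreme administration over years. Each step raises the share of children who cross the line through ordinary variation alone. One poor parent rating, for instance during an acute illness, is enough to date an event.

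The primary objective is to estimate incidence. Without a background figure beside it, a reader cannot tell how much of that incidence reflects treatment or transplant and how much the scoring rule would produce in any group of children. Cases that arise by chance occur in both arms, so they also shrink a true difference between blinatumomab and chemotherapy.

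**Working it through.** **Plan's own figure.** The protocol states no background rate for this definition, so there is nothing to reproduce.

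**Inputs from the protocol**
- Cut-off: 2 SD, any one domain (sections 8.1 and 9.3.1).
- Domains: section 9.3.1 names motor, language and social skills as adaptive domains. The BRIEF has three broad areas on the preschool and parent forms and two on the form for age 19 and over. That gives up to about 6 scores per administration; 4 is used as a low case.
- Motor from age 10: no normative rate is given for the age-equivalency rule. It is not modelled, and it could only add cases.
- Number of administrations, enrolment included, with enrolment close to transplant and complete follow-up:
  - enrolled at 2: 8 half-yearly steps to age 6, then 8 yearly steps to 14, giving 8 + 8 + 1 = 17
  - enrolled at 6: 12 + 1 = 13
  - enrolled at 17: yearly to the limit at age 25, giving 8 + 1 = 9

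**Assumptions.** Scores are normal. Correlation between domains is 0.5, 0.7 or 0.8. Correlation between visits is 0.6, 0.7, 0.8 or 0.9, the same for every pair of visits. The protocol gives none of these.

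**Simple bounds**
- One score: p = 1 − Φ(2) = 0.02275, or 2.3%.
- One administration, 6 independent domains: 1 − (1 − 0.02275)^6 = 12.9%. Positive correlation lowers this.

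**Simulation.** 60,000 norm-population children per combination, for 4 and 6 domains and all 12 pairs of correlations. A child is flagged if any score lies beyond 2 SD. Selected results, in percent:

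| Domains | Corr. between domains | Corr. between visits | 1 admin. | 3 admin. | 13 admin. | 17 admin. |
|---|---|---|---|---|---|---|
| 4 | 0.8 | 0.9 | 5.4 | 8.5 | 13.4 | 14.3 |
| 4 | 0.7 | 0.8 | 6.1 | 11.3 | 20.3 | 22.0 |
| 6 | 0.7 | 0.8 | 7.5 | 13.7 | 24.1 | 26.1 |
| 6 | 0.5 | 0.7 | 9.6 | 19.1 | 35.7 | 39.0 |
| 6 | 0.5 | 0.6 | 9.4 | 20.2 | 41.2 | 45.1 |

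Across all combinations this is about 5-10% at one administration, 9-20% over three and 13-46% over 13 to 17. The top value varies between 45% and 46% from run to run.

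**Dependence on the number of tests.** Going from 13 to 17 administrations adds 0.9 to 3.9 points. Going from 3 to 13 adds more: 13.4 − 8.5 = 4.9 points in the first row and 41.2 − 20.2 = 21.0 in the last.

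A second simulation followed the protocol's schedule by age: BRIEF only from age 2, two BRIEF areas from age 19, motor dropped from age 10. Share ever flagged with complete follow-up:

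| Enrolled at age | Corr. 0.5 / 0.7 | Corr. 0.7 / 0.8 | Corr. 0.8 / 0.9 |
|---|---|---|---|
| 2 (17 admin.) | 38% | 26% | 16% |
| 6 (13 admin.) | 34% | 23% | 15% |
| 17 (9 admin.) | 26% | 18% | 12% |

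**Dilution.** Suppose every truly impaired child is flagged, and chance flags arise at rate b independently of true impairment. The observed rate is then b + (1 − b)t for true rate t, so a difference between arms is multiplied by (1 − b). A true 10-point difference becomes 10 × (1 − 0.13) = 8.7 points at the low end and 10 × (1 − 0.46) = 5.4 points at the high end.

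**Effect of confirmation.** Requiring the same domain beyond 2 SD at two consecutive administrations gives about 7-15% over 13 to 17 administrations. The background falls but does not disappear.

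**The case against.** The strongest reply is that section 9.3.1 defines a score cut-off and never says that one score at any administration suffices. How repeated scores become an event is often left to the analysis plan, which is not at hand, and a scoring manual is promised. It is true that the any-administration reading is an inference. But it follows from incidence proportions and time to first onset, and nothing in the protocol points to another reading. The manual is described as covering administration and scoring, not event definition. The case rule of a primary endpoint is already fixed in the protocol.

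The protocol also has other views of the data. Section 9.6 says that scores and percentiles will be used in the final analysis, and section 9.3.1 adds change from the patient's own baseline. Both are useful additions. Neither puts a normative background beside the incidence, and the own-baseline rule also uses 2 SD without confirmation.

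A reader might infer three stronger conclusions, which the documents do not support:
- **That normal variation or testing frequency dominates the estimate.** The protocol gives no expected impairment rate for these patients, so the share due to chance cannot be stated. The gap between 13 and 17 tests is only about 1-4 points.
- **That the comparison between arms is biased in a known direction.** With similar follow-up, chance cases fall on both arms and dilute the contrast. Kaplan-Meier and Cox methods take account of length of follow-up. The crude proportions and the logistic model are more exposed.
- **That every child faces 13 to 17 tests.** Section 9.5 assumes 35% long-term survival, relapse and second malignancy censor, and follow-up stops at age 25. Many children will have fewer tests, which is why the figure for three administrations matters.

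Making two-visit confirmation the main definition would also be open to challenge. It gives up sensitivity in a safety study, and a patient who dies or drops out cannot be confirmed.

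**Conclusion.** The point stands as a weakness in a stated primary-endpoint rule. Followed as written, the rule would label about 5-10% of norm-population children impaired at one administration, 9-20% over three and 13-46% over 13 to 17. Even the most favourable combination at 13 administrations (13.4%) is more than five times the 2.3% for a single score. The consequences are an inflated absolute incidence and a diluted contrast between arms, with a modest dependence on how often and how long a child is tested.

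The mechanism comes from the protocol's own text. The size rests on assumed correlations and normal scores, and the upper range on complete follow-up.

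**What to change.** Keep the any-occurrence incidence, and state in sections 9.3.1 and 9.7.2.2.3 that it will be reported with:

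- **(a) Point prevalence** of scores beyond 2 SD, per domain and for any domain, at fixed times after alloHSCT (for example 1, 3, 5, 8 and 12 years), by arm and age band. Set it beside the normative expectation: about 2.3% per domain, and a higher any-domain rate taken from the norms or from simulation.
- **(b) A pre-specified confirmed-impairment analysis**: beyond 2 SD in the same instrument's domain at two consecutive administrations, dated at the first. BRIEF areas must be mapped across the preschool, parent and adult informant forms, because they differ. The text must also say how the motor rule from age 10 is confirmed.

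The cost is wording and a little more analysis; no new data are needed. In (b), an abnormal score at the last administration, or just before death or drop-out, stays unconfirmed. The interval to confirmation is also 6 months below age 6 and a year after. Keeping the any-occurrence incidence ensures that such scores are still counted.

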7.3 Statistical Inference

The study will compare blinatumomab therapy versus chemotherapy for the occurrence of neuropsychomotor developmental impairment, neurological impairment, endocrine impairment, and immune system impairment.

8. Research Question and Objectives

The overarching aim of this study is to describe and compare the long-term safety profile of B-precursor ALL paediatric patients who have been treated with either blinatumomab or chemotherapy prior to undergoing alloHSCT.

Primary 8.1

Primary Objective					
Objective	Endpoint				
 To estimate incidence of neuropsychomotor developmental impairment, endocrine impairment, neurological impairment, and immune system impairment (including auto-immune disorders and vaccine failure) 	 Impairment defined as any of the following: Neuropsychomotor development impairment in any area of social and emotional, language/communication, cognitive, or motor Neurologic impairment defined as any peripheral nervous system disorders including neuromuscular junction disorders; central nervous system disorders Endocrine impairment defined as any Hypothalamus-Pituitary-Gonadal Axis disorders; Hypothalamus-Pituitary-Adrenal (HPA) Axis disorders; Hypothalamus-Pituitary-Thyroid Axis disorders Immune system impairment defined as any leukopenia (neutropenia and/or lymphopenia); low IgG; low IgM, and; low IgA; autoimmune disorders; vaccination failure 				

8.2	Secondary
•	

• To estimate the incidence of Haemopoietic Stem Cell Transplant (HSCT) related adverse events (AEs)	 HSCT-related AEs defined as any second malignancy; Graft versus Host Disease (GvHD); infection, and/or; relapse
 To estimate the incidence of subsequent relapse of leukemia including in the central nervous system (CNS) 	 Relapse is defined as any of the following: Isolated bone marrow relapse (M3³ in the absence of extramedullary involvement) Combined bone marrow response (M2 or M3 marrow and at any extramedullary manifestation of ALL) Extramedullary relapse (either CNS relapse, testicular relapse, or relapse at other sites⁴)

³ Cytological bone marrow assessment grading: see Appendix F for details
 ⁴ See Appendix F for relapse criteria (including extramedullary relapse)

 To estimate the cumulative incidence of long-term AEs 	 AEs in any of the following organ systems: gastrointestinal, hematologic, dermatology, cardiac, pulmonary, hepatic, renal, neurological, infection, immunology, and skeletal

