9.2.1 Study Period

Enrolment of patients into 20180130 will occur if they meet all eligibility criteria. All eligible patients or their caregivers/legal guardians will be approached to provide informed consent for participation. Once informed consent has been given, and all inclusion/exclusion criteria are met, the patient will be enrolled via interactive response technology (IRT) in the study and data collection will begin. The study will commence at the first data collection of the first site. Patients will be followed for a maximum of a 12-year period or up to the age of 25 years, death, withdrawal of consent, or loss to follow-up, whichever comes first. The study will end when 12 years of follow-up for the last patient (if the patient has not withdrawn consent, been lost to follow-up, or died before the end of the 12 years of follow-up) is completed. If the last patient enrolled on study dies or is lost to follow-up before the 12 years following alloHSCT, the remainder

of the patients on study will continue to be followed until all patients on study have reached 12 years following alloHSCT, until death, withdrawal of consent, or lost to follow-up, whichever occurs first.

Data will be entered into an eCRF and will encompass information abstracted from patient charts from routine clinical visits. Data abstraction will be performed approximately every 6 months (± 30 days) starting at enrolment. Additional data on neuropsychomotor development will be assessed through specific questionnaires (paper and/or electronic) which will be administered at pre-specified intervals starting at enrolment (approximately every 6 months [± 30 days] for patients up to 6 years old and approximately yearly [± 60 days] for patients from 6 years old).

The first day of follow-up (day 1) will be the date of successful completion of alloHSCT (following chemotherapy/ blinatumomab treatment).

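### From age 10 the motor-impairment rule compares a score expected to plateau with a chronological age that keeps rising, so normally developed older patients are classed as impaired

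*Protocol*

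**What the plan says.** Section 9.3.1 sets a general rule for adaptive-functioning domains: impairment is a score 2 or more standard deviations below the normative mean. Motor skills get a different rule at older ages. From age 10, impairment is defined as "having an age-equivalency a year or more below their chronological age, as further development is not expected beyond that age"; limited normative data are given as a further reason.

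The Vineland-3 supplies the motor score at every age: "For all patients, the Vineland Adaptive Behavior Scales-Third Edition (Vineland-3) Comprehensive Parent/Caregiver Form will be used". On duration, Section 9.2.1 states: "Patients will be followed for a maximum of a 12-year period or up to the age of 25 years". Day 1 is the date of transplant.

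The motor result feeds a primary endpoint through the table in Section 8.1: "Neuropsychomotor development impairment in any area of social and emotional, language/communication, cognitive, or motor". One area is enough. Section 9.7.2.2.3 reports incidence proportions and Kaplan-Meier estimates of time to first onset.

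Section 9.3.1 also adds a within-person analysis, in which changes of 2 SD or more from a patient's "own baseline will be considered relevant adverse effects".

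**The concern.** The reason given for the rule argues against the rule. If motor development is essentially complete by about 10, the age-equivalent has nowhere further to go, but the yardstick gains a year every year. A healthy 15-year-old who scores at a plateau of 10 is five years behind by this definition, and a healthy 25-year-old is fifteen years behind.

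Because any single area makes a patient a case and only the first onset counts, one age-driven flag settles the neuropsychomotor endpoint for that patient. The flag occurs in both arms and does not depend on treatment. It raises the incidence, pulls the arms together, and makes time to onset largely a function of how old the patient was at transplant. The study is a category 1 commitment motivated partly by possible effects on the developing brain (Section 7.2), so this is a result that readers will look for.

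**Working it through.** The protocol gives no figure for the share of patients that the motor rule would flag, so there is none to reproduce. The only plan figure used below is the size per arm: 52/0.35 = 148.6, rounded up to 149 (Section 9.5).

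**Inputs**
- Rule: flagged if chronological age minus motor age-equivalent is 1 year or more (Section 9.3.1).
- C, the highest attainable motor age-equivalent: not printed. C = 10 follows from the rule's own reason; 11, 12 and 14 are tried as alternatives.
- Age mix: about equal numbers aged 0-2, 3-6, 7-12 and 13-17 (Section 9.5). Assumed uniform within each group, that is on 0 to 3, 3 to 7, 7 to 13 and 13 to 18 years.
- Follow-up: from transplant to year 12 or age 25, assumed complete.

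**Step 1: one normal patient.** Such a patient has an age-equivalent of min(age, C), so the gap is age − min(age, C), and it reaches 1 year at age C + 1. With C = 10 the gap is 1 year at 11, 5 at 15, 8 at 18 and 15 at 25.

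**Step 2: the cohort.** With a = age at transplant, the share of normal patients flagged by year t is the average over the four groups of P(a + t ≥ C + 1). For C = 10:
- Transplant (a ≥ 11): (0 + 0 + 2/6 + 1)/4 = 33%
- Year 4 (a ≥ 7): (0 + 0 + 1 + 1)/4 = 50%
- Year 8 (a ≥ 3): (0 + 1 + 1 + 1)/4 = 75%
- Year 10 (a ≥ 1): (2/3 + 1 + 1 + 1)/4 = 92%
- Year 12: 100%, since even a newborn is then 12

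**Step 3: other ceilings.**

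| C | Age at which flagged | At transplant | Year 4 | Year 8 | Year 12 |
|---|---|---|---|---|---|
| 10 | 11 | 33% | 50% | 75% | 100% |
| 11 | 12 | 29% | 46% | 69% | 100% |
| 12 | 13 | 25% | 42% | 63% | 92% |
| 14 | 15 | 15% | 33% | 50% | 75% |
| Open-ended top score | never | 0% | 0% | 0% | 0% |

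For comparison, a 2 SD rule would flag Φ(−2) = 2.3% of a normal population on motor skills, assuming normality.

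**Step 4: person-time, C = 10.** Mean years at age 11 or over are 2.5, 6, 10.67 and 9.5 in the four groups, out of 12, 12, 12 and 9.5 possible. The share is 28.67/45.5 = 63%.

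**Step 5: dilution.** If a share f is flagged on age alone in each arm, the observed rate is f + (1 − f) × true rate. True rates of 30% and 10% are assumed for illustration only (two-sided 5% test).

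| f | Observed rates | Power, 149 per arm | Power, 52 per arm |
|---|---|---|---|
| 0 | 30.0% vs 10.0% | 0.99 | 0.73 |
| 1/3 | 53.3% vs 40.0% | 0.64 | 0.27 |
| 0.75 | 82.5% vs 77.5% | 0.19 | 0.09 |
| 1 | 100% vs 100% | no contrast | no contrast |

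At f = 1 an odds ratio among completers cannot be estimated.

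**The case against.** **The ceiling is inferred.** The protocol says that further development is not expected and that norms are limited. It does not print a top age-equivalent or say how a top score is treated. This stands, and it is why the shares are given by ceiling. A reader might infer that every patient is flagged from age 11. That needs a ceiling of 10, which the protocol implies but does not state.

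**Scoring is delegated.** Section 9.3.1 promises a scoring manual by a study neuropsychologist, which could treat a ceiling score as unimpaired. That would cure the problem. But the protocol fixes the impairment definition itself and promises no ceiling rule. Section 9.6 says scores and percentiles will be used in the final analysis, which keeps the raw material for reclassification but does not withdraw the definition.

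**Full follow-up is a maximum.** Section 9.5 assumes 35% long-term survival, and Section 9.7.2.2.3 censors events after relapse or secondary malignancy. The 100% therefore applies only to patients who remain under observation. The equal age mix is something the sponsor will attempt, stated for long-term survivors. Patients flagged at their first assessment might also be treated as prevalent rather than incident cases; either way, this flag says nothing about treatment.

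**Age adjustment is planned.** Section 9.7.2.2.3 has covariate screening, adjusted models and propensity-score weighting, and Section 9.7.2.2.4 lists age subgroups. It would be too strong to say that any age difference between arms will appear as a treatment effect. Adjustment cannot, however, restore a contrast lost because nearly everyone is a case.

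**Two other stronger readings fail.** One is that the whole primary endpoint is lost. The social, language and executive-function rules are unaffected, within-person motor change can still be examined, and neurological, endocrine and immune impairment are separate. The other is that a 2 SD recovery is meant to count as harm. The within-person sentence names no direction, but it is introduced for patients who start above average and whose change the fixed cut-off would miss, so decline is clearly meant. Neutral wording also suits two scales on which worse runs in opposite directions.

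**Conclusion.** The motor rule for patients aged 10 and over is wrong as written; it is not a detail left for later. It follows from the protocol's own sentence that normally developed patients are classed as impaired once they are a year past the highest attainable motor age-equivalent.

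The size depends on that ceiling. Every finite value tried, from 10 to 14, leaves at least three quarters of normal patients flagged by the end of full follow-up; only an open-ended reading of the top score removes the problem. The figures rest on equal age groups, uniform ages within groups and no loss to follow-up. Deaths, dropout and censoring would lower the counts without correcting the rule. The damage is confined to the motor component at older ages and to the any-area neuropsychomotor endpoint built on it.

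**What to change.** In Section 9.3.1, for patients aged 10 and over, define motor impairment as an age-equivalent one year or more below the lower of (a) chronological age and (b) the highest motor age-equivalent attainable on the instrument, and state that a score at the ceiling counts as not impaired. Print the value of that ceiling and carry the same rule into the scoring manual. No normally developed patient at the plateau would then be flagged because of age.

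As a minor clarification in the same section, say that the within-person 2 SD rule means a change in the direction of worsening on each scale.

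The cost is one sentence for the rule, a few words for the clarification and a matching line in the manual. The questionnaires, visit schedule and sample size are unchanged, and no new data are needed.
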